2.10.2.1 General rules for AE reporting

The number and percentage of patients reporting any AE will be summarized by primary SOC, PT overall and by treatment group. The most common AEs reported (\geq xx% in any group for each preferred term; xx% depends on the total number of AEs) will be presented in descending frequency according to its incidence in EPO and EPO+DFX starting from the most common event.

Additional summaries will be provided by severity and relationship to study treatment.

If a patient reported more than one AE with the same preferred term, the AE with the greatest severity will be presented. If a patient reported more than one AE within the same primary system organ class, the patient will be counted only once with the greatest severity at the system organ class level, where applicable.

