4.1 Description of study design

This is an open-label, phase II, randomized, multi-center, pilot study to assess the efficacy in terms of erythroid improvement of DFX combined with EPO compared to EPO alone in patients with low- and int-1-risk MDS.

Patients will be randomly assigned to DFX plus EPO 40,000 units/week or to EPO 40,000 units/week alone in a 1:1 ratio. The dose of DFX DT will be 10 mg/kg/day and the dose of DFX FCT will be 7 mg/kg/day. At the time when DFX FCT study drug becomes available at a study site, all new patients who are randomized to combination therapy will receive the DFX FCT. Patients who are ongoing and receive DFX DT will continue with the DT. It is not permitted to change formulation during treatment. EPO dose changes after 4 and 12 weeks of study treatment will also be performed in both arms according to the EPO guidelines.

If after 4 weeks, increase in Hb is < 1 g/dL and total Hb is < 12 g/dL, the EPO dose will be increased to 60,000 units/week. If increase in Hb is ≥ 1 g/dL and total Hb is < 12 g/dL, patients will continue the current EPO dose. If Hb increase is ≥ 1 g/dL and total Hb is ≥ 12 g/dL, the patients will hold EPO treatment until end of study (Table 4-1).

If after 12 weeks of treatment with EPO alone, Hb increase is < 1 g/dL and total Hb is < 12 g/dL, the patient will switch to the combination therapy with EPO and DFX. If increase in Hb is ≥ 1 g/dL and total Hb is < 12 g/dL, patients will continue the current EPO dose. If Hb increase is ≥ 1 g/dL and total Hb is ≥ 12 g/dL, the patients will hold EPO treatment until end of study (Table 4-1).

[figure not shown]
If after 12 weeks of treatment with EPO in combination with DFX, Hb increase is < 1 g/dL and total Hb is < 12 g/dL, the patient will be discontinued from the study. If increase in Hb is ≥ 1 g/dL and total Hb is < 12 g/dL, patients will continue the current EPO dose plus DFX. If Hb increase is ≥ 1 g/dL and total Hb is ≥ 12 g/dL, the patients will hold EPO dose and receive treatment with DFX alone.

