	Hb increased < 1 g/dL from baseline and Hb < 12 g/dL	Increase EPO to 60,000 units/week *
	Hb increase is ≥ 1 g/dL and Hb < 12 g/dL	Continue EPO 40,000 units/week *
	Hb increase is ≥ 1 g/dL and Hb ≥ 12 g/dL	Hold EPO treatment *
Week 12	Hemoglobin status	Action
	Hb increased < 1 g/dL from baseline and Hb < 12 g/dL	If patient is in the combination arm: Discontinue from the study or If patient is in the EPO monotherapy arm: Switch to the combination EPO + DFX
	Hb increase is ≥ 1 g/dL and Hb < 12 g/dL	Continue current EPO dose *
	Hb increase is ≥ 1 g/dL and Hb ≥ 12 g/dL	Hold EPO treatment *

* Patients in combination arm will continue DFX DT 10 mg/kg/day or DFX FCT 7 mg/kg/day treatment

[figure not shown]
The primary objective (erythroid response according to IWG criteria: Hb increase ≥ 1.5 g/dL) will be assessed at 12 weeks of treatment. At any time, if Hb ≥ 12 g/dL, EPO will be stopped until the end of study.

At 24 weeks, patients initially assigned to the combination therapy who showed Hb increase ≥ 1 g/dL at week 12 will be assessed for full hematological response according IWG criteria (Erythroid response: Hb increase from baseline ≥ 1.5 g/dL; Neutrophil response: increase from baseline of ≥ 100% and > 0.5 x 10⁹/L; Platelet response: increase from baseline of ≥ 30 x 10⁹/L). Patients initially treated with EPO alone and switched to the combination therapy with EPO and DFX after 12 weeks will be assessed for erythroid response according to IWG criteria after 24 weeks.

No RBC transfusions are allowed after randomization, as transfusions would affect the endpoints of the trial. Patients who are RBC transfusion dependent must not be enrolled in the study. RBC transfusion dependence is defined as more than 2 units RBC /4 weeks at any time during the last 12 week period prior to study entry (Gale 2011). Patients must be withdrawn from the study anytime when transfusion as rescue therapy is needed.

Safety assessments are routinely performed including collection of AEs, SAEs, vital signs, physical examination, ECG, hematological and biochemistry assessments.

Patients will continue therapy until disease progression or intolerable toxicity, patient decision or death, after 12 weeks of combination treatment without response or after 24 weeks treatment duration at which point an End of Treatment (EOT) Visit will be performed and the End of Treatment CRF page will be completed.

30 day follow-up

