2.5 Statistical methods and data analysis

Categorical parameters

Categorical (qualitative) data (e.g., gender, race, etc) will be presented as frequencies and percentages. A missing category for categorical data will be presented where applicable. Unless otherwise noted, percentages will be based on the number of patients in the relevant population or subgroup as the denominator. Categorical variables will be summarized by absolute and relative frequencies where applicable.

Continuous parameters

Continuous (quantitative) data (e.g., age, body weight, etc.) will be summarized by number of patients, mean, standard deviation, median, minimum, and maximum. The lower and upper quartiles may also be used under special circumstances.

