2.10.2 Adverse events (AEs)

The reporting of AEs and AEs of special interest will be reported in the following periods based on the treatment received as follows:

- For patients receiving EPO during the first 12 weeks and for those continuing with EPO after 12 weeks (no switching to EPO+DFX arm), the safety data will be reported based on the corresponding treatment group: EPO. The safety data will be reported in period 1-12 weeks, 13-24 weeks and 1-24 weeks.
- For patients receiving EPO+DFX DT or EPO+DFX FCT from week 1 and continuing with EPO+DFX DT or EPO+DFX FCT after 12 weeks or with DFX DT or DFX FCT alone after 12 weeks, the safety data will be reported based on the corresponding treatment group EPO+DFX. The safety data will be reported in period 1-12 weeks and 1-24 weeks.
- For patients receiving EPO alone and switched to EPO+DFX after 12 weeks of treatment, the safety data will be reported only in period 13-24 weeks.

Overall summary will be reported for AEs occurred in period 1-12 weeks of treatments and 1-24 weeks for patients receiving EPO alone and patients receiving EPO+DFX DT or EPO+DFX FCT.

Overall summary, SAE and AEs leading to study drug discontinuation will be reported for in the corresponding treatment: EPO, DFX DT, DFX FCT, EPO+DFX DT and EPO+DFX FCT.

All AEs will be coded using the latest version of MedDRA at the time of analyzing data using the Safety Set. The severities of the AE will be coded as mild/moderate/severe as documented in the CRF.

Summary tables for AEs have to include only AEs that started or worsened during the on-study period, the treatment-emergent AEs, i.e. TEAEs. However, all safety data (including

those from the pre and post-study periods) will be listed and those collected during the pre-study and post-study period will be flagged.

If an AE deteriorates or improves over time, new event will be reported accordingly with new severity.

The incidence of treatment-emergent AEs (new or worsening from baseline) will be summarized by system organ class and or preferred term, severity (mild/moderate/severe), type of AE and relation to study treatment.

Deaths reportable as SAEs and non-fatal serious AEs will be listed by patients and tabulated by type of AE.

Additionally, AEs and SAEs with suspected relationship to study drug, requiring dose adjustment, leading to drug interruption/discontinuation, requiring significant additional therapy will be specifically tabulated and listed.

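### Weeks 1-24 AE percentages compare columns whose time at risk differs by rule, and the likely effect is to understate AE risk on the combination

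*SAP*

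**What the plan says.** **Measure.** SAP 2.10.2.1: "The number and percentage of patients reporting any AE will be summarized by primary SOC, PT overall and by treatment group". SAP 2.5 makes patients, not patient-time, the denominator: "percentages will be based on the number of patients in the relevant population or subgroup as the denominator".

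**Week-12 rule.** Protocol 4.1 (Table 4-1, repeated in SAP Table 2-1) treats the same result, an Hb rise below 1 g/dL with Hb below 12 g/dL, differently by arm: "If patient is in the combination arm: Discontinue from the study", but "If patient is in the EPO monotherapy arm: Switch to the combination EPO + DFX".

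**Reporting periods (SAP 2.10.2).**
- EPO patients who do not switch: "The safety data will be reported in period 1-12 weeks, 13-24 weeks and 1-24 weeks".
- EPO+DFX from week 1: "The safety data will be reported in period 1-12 weeks and 1-24 weeks". No separate weeks 13-24 view is listed.
- EPO patients who switch: weeks 13-24 only.

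The section then adds, for EPO alone and EPO+DFX: "Overall summary will be reported for AEs occurred in period 1-12 weeks of treatments and 1-24 weeks".

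**AE window.** SAP 2.10.1 ends the on-treatment period 30 days after the last dose.

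**Exposure.** SAP 2.7.1 and 2.7.2 tabulate duration of exposure separately. Neither document uses it in an AE incidence.

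**The concern.** Tolerability and safety of the combination is a listed secondary objective (Protocol Table 3-1). A crude percentage over weeks 1-24 compares groups fairly only if they are observed for similar lengths of time. Here a rule removes some combination patients halfway. The EPO patients with the same Hb result are taken out of the EPO weeks 1-24 column, which leaves patients planned to stay for 24 weeks.

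The weeks 1-12 table is fair on time but cannot show later events. For patients randomised to the combination, the listed periods put events after week 12 only in the weeks 1-24 table, where the imbalance lies. SAP 2.10.2.1 also orders the common AEs by incidence in EPO and EPO+DFX, so readers will compare the two columns.

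**Working it through.** The documents give no AE rate, no expected share leaving at week 12 and no exposure-adjusted figure, so there is no planned figure to reproduce. What follows is an illustration under stated assumptions.

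**Inputs from the documents**
- Treatment lasts 24 weeks (SAP 2.2).
- Leavers stop at week 12 (Protocol 4.1).
- AEs count to last dose + 30 days (SAP 2.10.1), so leavers are at risk to 12 + 30/7 = 16.3 weeks.
- Completers are capped at week 24, because the table is labelled weeks 1-24.

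**Assumptions**
- The hazard of a first event, h, is constant and equal in both groups; h = 0.02 per week, varied below.
- The share of combination patients leaving at week 12, f, is 30%, 45% or 60%. The 40% reference response rate in SAP 2.11 (rise of at least 1.5 g/dL) would put f at roughly 60% or less, because patients with a rise of 1 to below 1.5 g/dL stay.
- Leavers remain in the EPO+DFX column.

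**Formulas**
- EPO column: 1 - exp(-24h)
- EPO+DFX column: (1-f)(1 - exp(-24h)) + f(1 - exp(-16.3h))

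**Result at h = 0.02.** Risk to week 24 is 1 - exp(-0.48) = 38.1%. Risk to week 16.3 is 1 - exp(-0.326) = 27.8%. The gap is f × 10.3 points.

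| f | EPO | EPO+DFX | Gap (points) |
|---|---|---|---|
| 30% | 38.1% | 35.0% | 3.1 |
| 45% | 38.1% | 33.5% | 4.6 |
| 60% | 38.1% | 31.9% | 6.2 |

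**Other hazards, same formulas.** At h = 0.01 the gaps are 1.9, 2.8 and 3.8 points. At h = 0.04 they are 4.2, 6.2 and 8.3 points.

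**Check 1: EPO-alone patients who stop EPO.** Under Protocol 4.1 an EPO-alone patient reaching Hb 12 g/dL or above stops EPO to study end, while a combination patient continues DFX. If the AE window closes 30 days after the last EPO dose, the EPO column also loses time. Assume 30% of that column stops at week 12: its risk is 0.7 × 38.1% + 0.3 × 27.8% = 35.0%, and the gap at f = 45% falls from 4.6 to 1.5 points. If they stop at week 8, the window ends at week 12.3 and the gap becomes -0.3 points.

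**Check 2: early AEs.** Take a hazard of 0.08 per week for weeks 1-4 and 0.005 after, in both groups, with f = 45%. Crude percentages are 34.3% for EPO and 33.1% for EPO+DFX, so the gap nearly closes. A single weeks 1-24 exposure-adjusted rate is then about 12% higher on the combination at identical risk: first events per week at risk are 0.343/17.24 = 0.0199 for EPO and 0.331/14.92 = 0.0222 for EPO+DFX. A rate needs to be split by period.

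**The case against.** The strongest reply has five parts.

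1. **Direction.** The EPO stopping rule at Hb 12 g/dL or above works the other way, and SAP 2.9.2.4 describes the non-switchers as responders, so such patients may be common in the EPO column. This stands. How much it matters depends on SAP 2.10.2, which counts AEs in an on-study period that SAP 2.10.1 does not define. If patients who stopped EPO are counted to study end, the offset disappears.
2. **Column membership.** SAP 2.10.2 describes the EPO+DFX group as starting at week 1 and continuing after week 12. Read literally, leavers are outside the column and the bias vanishes, but their AEs then belong to no listed group. The Safety Set rule in SAP 2.10 and the overall-summary sentence favour including them. The text does not settle it, which is itself a reason to amend.
3. **Timing.** The protocol suggests some early onset: severe hypersensitivity mostly in the first month (6.3.1.7), and gastrointestinal and skin reactions generally transient (1.2.1.2). This stands and shapes the remedy.
4. **Existing safeguards.** A weeks 1-12 table, exposure tables and listings showing true treatment at AE onset are planned. The table shells sit in Module 7, which is not available here, so missing footnotes cannot be asserted. None of the planned items seen adjusts the weeks 1-24 percentages.
5. **Scale.** This is a pilot of about 60 patients with no AE test. At 30 per arm and a risk near 35%, the 95% half-width for a difference is 1.96 × √(2 × 0.35 × 0.65/30), about 24 points. Random error dominates. That lowers the priority, but it does not justify a systematic difference that is cheap to avoid.

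**Conclusion.** The concern holds in a limited form. The weeks 1-24 columns differ in time at risk by rule, nothing in either document adjusts AE incidence for it, and the likely direction is to understate AE risk on the combination. The size is about 3 to 6 points at h = 0.02. That rests on an equal constant hazard, assumed leaving shares of 30% to 60%, and leavers being kept in the EPO+DFX column.

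A reader might infer more: that the combination must look safer at equal risk, that the gap is about 7.5 points at 45% leaving (30.6% against 38.1%), and that all of it is artefact. The documents do not support this. The 7.5 stops counting leavers' AEs at week 12, whereas SAP 2.10.1 counts them for 30 more days. The EPO stopping rule can offset or slightly reverse the direction. Early-clustered AEs shrink the gap. Neither the hazard nor the leaving share is given in the documents. This is an inexpensive improvement to a stated safety objective and does not touch the primary analysis.

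**What to change.** In SAP 2.10.2 and 2.10.2.1:

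1. **Membership.** State that all Safety Set patients who started EPO+DFX, including week-12 leavers, are in the EPO+DFX weeks 1-24 column. State where switchers' weeks 1-12 data are counted; the comparison in item 2 needs them in the EPO arm.
2. **Comparison of percentages.** Name weeks 1-12 by randomised arm as the between-arm comparison, and footnote that weeks 1-24 percentages are not comparable between columns.
3. **Time at risk.** In the weeks 1-24 AE, SAE and AESI tables show total patient-weeks at risk and exposure-adjusted first-event incidence with 95% CI, split into weeks 1-12 and 13-24. This adds the missing weeks 13-24 view for patients randomised to the combination and keeps early-onset AEs from distorting a single rate.

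The cost is a little more programming. The dosing dates are already collected (SAP 4.2.2 and 4.2.3) and trial conduct does not change. Exposure adjustment does not remove selection of the EPO column on response, so the weeks 13-24 rates remain descriptive.

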2.10.3 Laboratory data

All laboratory values will be converted into SI units and the severity grade calculated using the low/normal/high classifications based on laboratory normal ranges and for selected parameters by notable and extended ranges as available in the deferasirox program standards.

Note that, Hemoglobin (g/dL) and Serum Ferritin (ng/mL) are the only exceptions which will be reported in US-units (if appropriate).

Table 2-4 Criteria for clinically notable and extended laboratory ranges

Parameter	Criteria
Absolute neutrophils	<1.5×10 ⁹ /L (extended range <0.5×10 ⁹ /L)
Platelets	<100×10 ⁹ /L (extended range <50×10 ⁹ /L)
ALT/AST	>5×ULN and >2×baseline value (extended range >10×ULN and >2×baseline value)
Serum creatinine	> 33% increase from baseline and >ULN at two consecutive measurements at least 7 days apart
Creatinine clearance	<60 mL/min at two consecutive measurements at least 7 days apart (extended range <40 mL/min)
Urinary total protein/creatinine ratio	>113.1 mg/mmol at two consecutive measurements at least 7 days apart

The frequency of laboratory abnormalities will be displayed by parameter and treatment group. Laboratory data will be summarized by presenting summary statistics of raw values at baseline and changes from baseline (absolute) to worst post-baseline value and by treatment group.

Laboratory data will be summarized by presenting **shift tables** showing baseline versus most extreme post-baseline result by notable range.

Box plots of absolute value will be provided for selected parameters.

Listings of all laboratory data with values flagged corresponding to normal/notable/extended ranges will be provided. The listing of all laboratory values will be provided by planned and actual dose along with the columns for treatment arm to which the patient was randomized and the treatment arm where the patient belongs at the time of the assessment will be provided.

Hematology:

Box plots on absolute value for Hb, neutrophil and platelets corresponding to each visit will be provided.

Absolute change from baseline to worst post-baseline value (the lowest for hematology parameters) will be provided for Hb, neutrophil and platelets.

Absolute change from baseline to last available value at the time of EOT will be provided for Hb, neutrophil and platelets.

Listings will be provided for Hb, platelets and neutrophils as well.

Only listings will be provided for the parameters: Hematocrit, red blood cell (RBC) count, reticulocyte count, mean corpuscular volume (MCV), White blood cell (WBC) count with differential.

Blood chemistry

Absolute change from baseline to worst post-baseline value (the highest for blood chemistry parameters except creatinine clearance, which the lowest value is considered to be the worst) will be provided for serum ferritin, ALT, AST, total bilirubin, serum creatinine, creatinine clearance and urinary protein/creatinine ratio.

Absolute change from baseline to last available value at the time of EOT will be provided for serum ferritin, ALT, AST, total bilirubin, serum creatinine, creatinine clearance and urinary protein/creatinine ratio.

Shift tables from baseline to post-baseline value will be provided for serum ferritin, ALT, AST, serum creatinine, creatinine clearance and urinary protein/creatinine ratio in the following way:

Serum ferritin - Baseline categories: ≤ 270 ng/mL, $> 270 - 500$ ng/mL, $> 500 - 1650$ ng/mL, > 1650 ng/mL and Missing;

Serum ferritin - Post-baseline categories: ≤ 270 ng/mL, $> 270 - 500$ ng/mL, $> 500 - 1650$ ng/mL, > 1650 ng/mL.

ALT/AST - Baseline categories: \leq ULN, $> ULN - \leq 5 \times ULN$, $> 5 \times ULN - \leq 10 \times ULN$, $> 10 \times ULN$ and Missing;

ALT/AST - Post-baseline categories: \leq ULN, $> ULN - \leq 5 \times ULN$, One value $> 5 \times ULN$, One value $> 10 \times ULN$, Two consecutive values measured at least 7 days apart $> 5 \times ULN$, Two consecutive values measured at least 7 days apart $> 10 \times ULN$, $> 5 \times ULN$ and $2 \times$ Baseline value, $> 10 \times ULN$ and $2 \times$ Baseline value and Missing.

Serum creatinine - Baseline categories: \leq ULN, $>$ ULN and Missing;

Serum creatinine - Post-baseline categories: \leq ULN, One value $>$ ULN, Two values $>$ ULN, Two consecutive values measured at least 7 days apart $>$ ULN, Two consecutive values measured at least 7 days apart $>$ ULN, both $>$ 33% increase from baseline and Missing-

Urinary protein/creatinine ratio – Baseline categories: ≤ 22.62 mg/mmol, $>22.62 - \leq 113.1$ mg/mmol, > 113.1 mg/mmol and Missing; Post-baseline categories: ≤ 113.1 mg/mmol, One value > 113.1 mg/mmol, Two values > 113.1 mg/mmol, Two consecutive values measured at least 7 days apart > 113.1 mg/mmol and Missing.

Creatinine clearance - Classification I:

Creatinine clearance - Baseline categories: < 40 mL/min, $40 - < 60$ mL/min, $60 - < 90$ mL/min, $90 - < 160$ mL/min, ≥ 160 mL/min and Missing;

Creatinine clearance - Post-baseline categories: Two consecutive values measured at least 7 days apart < 60 mL/min, One value < 60 mL/min, Two consecutive values measured at least 7 days apart $60 - <90$ mL/min, One value $60 - <90$ mL/min, two consecutive values measured at least 7 days apart $90 - < 160$ mL/min, One value $90 - <160$ mL/min, ≥ 160 mL/min and Missing.

Creatinine clearance - Classification II:

Creatinine clearance - Baseline categories: < 40 mL/min, 40 - < 60 mL/min, 60 - < 90 mL/min, 90 - < 160 mL/min, ≥ 160 mL/min and Missing;

Creatinine clearance - Post-baseline categories: Two consecutive values measured at least 7 days apart < 40 mL/min, One value < 40 mL/min, Two consecutive values measured at least 7 days apart 40 - <60 mL/min, One value 40 - <60 mL/min, ≥ 40 mL/min and Missing

Calculation for CrCl:

In the formula below, CrCl denotes creatinine clearance, SCr denotes serum creatinine in μmol/L; age in years will be calculated from date of birth and date of the relevant blood sample. Weight and height will be the last available measurements at the time of the relevant blood sample.

Cockcroft-Gault formula (≥18 years of age),

CrCl (mL/min) =

Male patients: $(140 - \text{age}) \times \text{weight} / (815 \times 0.001 \times \text{SCr})$

Female patients: $(140 - \text{age}) \times \text{weight} \times 0.85 / (815 \times 0.001 \times \text{SCr})$

Note 1: The recalculated creatinine clearance in derived Lab data and standard UNITCONV data:

- Parameter names (PARNAM1C) as 'CRCLSCG' for Cockcroft-Gault formula.
- Preferred (PREUNT1C) and Converted (CNVUNT1C) unit 'mL/min' for Cockcroft Gault formulae.
- Zero Precision (CNVPCS1N) for converted values.

Note 2: For Height and Weight, last available values at the time of assessments should be used. Current age should be derived at the time of assessments.

Listings will also be provided for serum ferritin, ALT, AST, total bilirubin, serum creatinine, creatinine clearance and urinary protein/creatinine ratio.

A listing of all laboratory values will be flagged as appropriate and will be provided along with planned and actual dose (EPO and EPO + DFX). Assessment day relative to first dose of study drug will be included.

All other blood chemistry parameters apart from the ones mentioned above will only be listed.

For the laboratory result on serum pregnancy: β-HCG and on urine pregnancy, listings will be provided.

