6.3.1.2 Elevations in serum creatinine

Serum creatinine should be monitored during the study as stated in the visit evaluation schedule [Table 7-1](#).

During the treatment period, patients who develop an increase in serum creatinine $\geq 33\%$ above their baseline value (average of visit 1 and 2) resulting in a serum creatinine above the upper limit of normal (ULN), on two consecutive occasions, the dose of the study drug will be reduced to 5 mg/kg/day for DFX DT and 3.5 mg/kg/day for DFX FCT until serum creatinine returns to below the age adjusted ULN.

It is recommended to check fluid balance and ensure adequate hydration of the patient.

In case of a single increase in serum creatinine, the assessment will be repeated in 2 weeks.

If after a dose reduction, a progressive increase in serum creatinine beyond the age adjusted ULN is observed, a treatment interruption is recommended.

After an interruption, if serum creatinine falls below the age appropriate ULN range on two consecutive visits, it is recommended to resume DFX DT therapy at 5 mg/kg/day or DFX FCT therapy at 3.5 mg/kg/day, and after 1 month, if the serum creatinine increase does not recur, study medication can be re-escalated to the standard dose of DFX DT at 10 mg/kg/day or DFX FCT at 7 mg/kg/day.

Caution should especially be used in patients with CrCl between 40 and less than 60 mL/min, particularly in cases where there are additional risk factors that may impair renal function such as concomitant medications, dehydration, or severe infections.

DFX therapy must be discontinued in case serum creatinine >2 times the age-appropriate upper limit or if CrCl <40 mL/min.

[figure not shown]
If after dose reduction, a progressive increase in serum creatinine is observed, Novartis must be contacted.

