Serum Creatinine ⁵	D	7.2.2.4.2	X	X	X	X	X	X	X		X	X	X	X	X		
ALT/AST	D	7.2.2.4.2	X	X	X	X	X	X	X		X	X	X	X	X		
Direct/Indirect/Total bilirubin	D	7.2.2.4.2	X	X	X	X	X	X	X		X	X	X	X	X		
Alkaline phosphatase	D	7.2.2.4.2	X	X	X	X	X	X	X		X	X	X	X	X		
Creatinine Clearance ⁶	D	7.2.2.4.2	X	X	X	X	X	X	X		X	X	X	X	X		
Urine dipstick ⁷	D	7.2.2.4.3	X		X	X	X	X	X		X	X	X	X	X		
Microscopic urine ⁷	D	7.2.2.4.3	Only if medically indicated in case of positive dipstick														
Urinary protein/creatinine ratio	D	7.2.2.4.3	X	X	X	X	X	X	X		X	X	X	X	X		
Serum pregnancy test ⁸	D	7.2.2.4.4		X											X		
Urinary pregnancy test ⁸	D	7.2.2.4.4			X				X		X	X	X	X			
Blood pressure self-monitoring ¹	S		-----continuous-----														

Visit	Category	Protocol Section	Screening 1	Screening 2	Treatment Period											Follow-up period	
					Randomization	Cycle 1		Cycle 2		Cycle 3	Cycle 4	Cycle 5	Cycle 6	End of study treatment (EOT)	30-day Safety Follow-up	Study evaluation completion	
Week			1	2	3	4	5	6	7	8 ³	9	10	11	12	777	501	778
Concomitant medication	D	6.4	X	X	X	X	X	X	X		X	X	X	X	X		
Adverse events ¹⁰	D	8.1	X	X	X	X	X	X	X	X	X	X	X	X	X	X	
Drug Dispensing	D	6.6.3			X				X		X	X	X	X			
Drug Accountability DFX	D	6.6.3							X		X	X	X	X	X		
Drug Accountability EPO	S	6.6.3							X		X	X	X	X	X		
Study Evaluation completion (SEC)	D																X

¹ Blood pressure has to be measured before each dose of EPO. EPO needs to be hold if BP >160/80.
² Ocular and Audiometry examinations must be performed at screening, should a patient have evidence at the Screening Visit that the examination(s) were performed 6 months prior to screening then the examination(s) do not need to be repeated. The examination(s) can be performed at any time at the investigators discretion if symptomatically/clinically indicated.
³ Visit 8 has to be performed only if EPO dose was increased at Visit 7. Then hematology parameters have to be assessed at Visit 8.
⁴ Serum ferritin: Two samples at screening done at least 14 days apart. The serum ferritin samples should be obtained in the absence of known infection.
⁵ Serum creatinine will be measured at Screening Visit 1 and Screening Visit 2 and the mean value will be used for eligibility criteria. Serum creatinine will also be measured weekly between the Randomization Visit and Week 4 visit.
⁶ Creatinine clearances will be calculated by the central laboratory at every visit.

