4.2.11 Visit Windows

A year = 365.25 days.

A month = 365.25/12=30.4375 days.

Month 1 = Day (1;45] and then floor(n×30.4375) days±15 days, n=2, 3, 4,... that is Month 2 = Day (45;75]; Month 3 = Day (75;106]; etc.

For each parameter (i.e., hematologic and erythroid response), time windows will be used to identify data to be considered for the specific analysis at a specific time point. If there is more than one assessment within the time window, the last available assessment in that time window will be used. For all windows after baseline, only values after first dose of study drug will be used. Time windows are defined based on date of randomization (=study day 1; Visit 3 according to VES of protocol).

The following table shows the time windows for the analyses of responses based on planned assessment schedule.

Table 4-1 Visit windows

Planned assessment	Time window	Nominal day for visit
Baseline	Baseline; see definition 4.2.6	Baseline
Visit 3: Date of Randomization	Day 1	Day 1
Visit 4	Day 4 to Day 10*	Day 7
Visit 5	Day 11 to day 17*	Day 14
Visit 6	Day 18 to Day 24*	Day 21
Visit 7	Day 25 to Day 31*	Day 28
Visit 8	Day 35 to Day 49*	Day 42
Visit 9	Day 50 to Day 63*	Day 56
Visit 10	Day 77 to Day 91*	Day 84
Visit 11	Day 105 to Day 119*	Day 112
Visit 12	Day 133 to Day 147*	Day 140

The End of Treatment visit time window is Day 161 to Day 175 with nominal day of visit is Day 168 considering Visit 3 as Day 1.

In case of early treatment discontinuation or end of visit 12, the follow up will be 27-33 days from the last date when a non-zero dose of study treatment is administered (Last date of study treatment).

Considering, a patient has received EPO only and received a response. This patient will hold EPO until study end. However, Follow-up visit for them will be 30 days (+/- 3 days after EOT) and not 27-33 days from the last date when a non-zero dose of study treatment is administered.

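### The SAP's notable-creatinine count requires readings at least 7 days apart, a condition absent from the protocol's dose-reduction trigger and from SAP deviation S12, so no table counts patients meeting the trigger in both arms

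*SAP*

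**What the plan says.** **SAP 2.10.3, Table 2-4.** Serum creatinine is notable for a > "33% increase from baseline and >ULN at two consecutive measurements at least 7 days apart". In the creatinine shift table of the same section, only one post-baseline category uses the 33% criterion, and it too requires two consecutive values at least 7 days apart. The weaker categories (one value above ULN, two values above ULN) have neither the spacing condition nor the 33% criterion.

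**Protocol 6.3.1.2.** The trigger is a rise of at least 33% over baseline, "resulting in a serum creatinine above the upper limit of normal (ULN), on two consecutive occasions". No interval between the occasions is given. The section adds: "In case of a single increase in serum creatinine, the assessment will be repeated in 2 weeks".

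**SAP Table 4-7, S12.** The deviation for not reducing deferasirox repeats the protocol trigger, at 33% or more on two consecutive occasions, again without spacing.

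**Protocol Table 7-1, footnote 5.** "Serum creatinine will also be measured weekly between the Randomization Visit and Week 4 visit".

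**SAP 4.2.11, Table 4-1.** Visits 4 to 7 have nominal Days 7, 14, 21 and 28. The windows for the last three are "Day 11 to day 17", "Day 18 to Day 24" and "Day 25 to Day 31". The section presents these windows as serving the response analyses.

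**The concern.** The weekly first-month tests are the plan's closest watch on renal function after DFX starts. The notable-value table should therefore show how many patients in each arm had a confirmed rise of the size the protocol acts on. The SAP's definition is stricter in two ways: more than 33% rather than at least 33%, and a 7-day minimum gap on a schedule whose nominal gap is exactly 7 days. A sample taken one day early relative to the previous one removes the pair.

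Two features make this more than wording. First, DFX is reduced after the second raised reading, and protocol 1.2.1.2 reports that some creatinine increases eased on a lower dose. A third raised reading, which could form a qualifying pair, is then less likely in patients on DFX, and no such mechanism acts on EPO alone. Second, a patient can meet the trigger, and be an S12 deviation if the dose is not reduced, without being notable in the laboratory table. The SAP then disagrees with itself as well as with the protocol.

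**Working it through.** **1. Definitions side by side**

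| Source | Size of rise | Also above ULN | Minimum gap |
|---|---|---|---|
| Protocol 6.3.1.2 | ≥33% | yes, two consecutive occasions | none |
| SAP S12 | ≥33% | yes, two consecutive occasions | none |
| SAP Table 2-4 | >33% | yes, two consecutive measurements | 7 days |
| SAP shift table, 33% category | >33% | yes, two consecutive values | 7 days |

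Baseline is not a source of difference: protocol 6.3.1.2 and SAP 4.2.9 both use the mean of Visits 1 and 2.

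**2. Which pairs are exposed**

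Taking the Table 4-1 windows at face value, the gap between adjacent weekly visits runs from 11 − 10 = 1 day to 17 − 4 = 13 days. It is the same for Visits 4–5, 5–6 and 6–7. From Visit 7 to Visit 9, the next scheduled chemistry, the gap is 50 − 31 = 19 to 63 − 25 = 38 days, so the condition is always met. Only the weekly first-month pairs are exposed.

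The two-week repeat after a single rise would satisfy the 7-day rule. For a rise first seen at Visit 4, 5 or 6, however, a scheduled weekly sample falls in between, so the first reading and the two-week repeat are not consecutive.

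**3. Share of two-reading rises missed**

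Let e₁ and e₂ be the deviations from the nominal day at two adjacent weekly visits. The gap is 7 + e₂ − e₁, and the pair fails when e₂ < e₁. If the deviations are independent with the same distribution, P(fail) = [1 − P(e₁ = e₂)]/2, which is always below 50%. The documents give no distribution of visit days, so each row is an assumption.

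| Assumed visit-day spread | P(e₁ = e₂) | Missed |
|---|---|---|
| All on the nominal day | 1 | 0% |
| 90% on day, rest even over the other six days | 0.9² + 6 × (0.1/6)² = 0.8117 | 9.4% |
| 70% on day, rest even over the other six days | 0.7² + 6 × 0.05² = 0.505 | 24.8% |
| Uniform, ±1 day | 1/3 | 33.3% |
| Uniform, ±3 days | 1/7 | 21/49 = 42.9% |

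**4. Longer rises**

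A run of raised weekly readings is missed only if every adjacent gap is under 7 days, that is, if the deviations strictly decrease. Under uniform ±3 days this is 35/343 = 10.2% for three readings and 35/2401 = 1.5% for four. Under uniform ±1 day it is 1/27 = 3.7% for three.

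**5. Without the spacing condition**, as in the protocol trigger and S12, the share missed because of spacing is 0% in every row.

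**The case against.** The strongest reply is that these rises are reported elsewhere. If DFX is reduced, the patient enters the dose-reduction tables with the reason (SAP 2.7.3). The abnormality is also an adverse event because it required a change in study medication (protocol 8.1.1 and 8.1.2), and adverse events requiring dose adjustment are tabulated (SAP 2.10.2). If DFX is not reduced, S12 records it. The values also appear in change to worst value, in the >ULN shift rows and in the listings with assessment day. All of this stands, so a reader who infers that such rises are never counted, or that the safety report as a whole understates renal toxicity, goes beyond the documents. But the dose-reduction and S12 routes exist only for patients on DFX and give no matching count for EPO alone. The >ULN rows have no 33% criterion, and listings are not a count by arm.

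A reader might also take the ±3-day windows as permitted visit tolerances and conclude that many rises are lost. Table 4-1 assigns data to time points for response analyses. The documents state no scheduling tolerance for these visits, and an on-schedule pair qualifies. The 43% is therefore one end of an assumed range that starts at 0%.

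Finally, the notable ranges come from the deferasirox program standards, and a reporting threshold need not equal a dosing trigger. That is fair, and it is a reason to let the standard row stay. It does not explain why the SAP uses the unspaced definition in S12 and never tabulates it.

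**Conclusion.** The mismatch is real but limited. SAP Table 2-4 and the one 33%-based shift category omit some first-month rises that meet the protocol trigger and S12, and no table counts patients meeting that trigger in both arms. For a rise seen at exactly two weekly visits, the share missed is 0% on schedule, about 9% with 90% of visits on the nominal day, and 33% to 43% under uniform spreads of ±1 and ±3 days. It is about 10% for three raised visits under ±3 days. These figures assume independent visit-day deviations with distributions that the documents do not supply. The effect on the comparison between arms is plausible, because dose reduction acts only on DFX, but it cannot be sized from the documents.

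A reader might extend the point to creatinine clearance and the urinary protein/creatinine ratio, which carry similar 7-day conditions. The documents do not support that: the two-consecutive trigger in protocol 6.3.1.2 concerns serum creatinine only.

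This is a cheap improvement to a descriptive safety table. It does not touch the primary analysis.

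**What to change.** Keep the program-standard notable row if wanted. Add to the creatinine notable and shift tables in SAP 2.10.3, by treatment group, the number of patients with creatinine at least 33% above baseline and above ULN at two consecutive measurements, scheduled or unscheduled, regardless of spacing. This matches protocol 6.3.1.2 and S12. Unscheduled samples must be included because the protocol speaks of occasions, and after the first month its two-week repeat falls between four-weekly visits. No minimum gap should be introduced, since the trigger has none.

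The passages on two consecutive occasions, on the repeat in 2 weeks and on readings at least 7 days apart should be reconciled. No clinical rule is proposed or changed here.

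The cost is one line of SAP text, one more programmed row and a few more flagged patients.
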